## 4 Selection and enrollment of participants

### 4.1 Inclusion criteria

Inclusion criteria for the study are:

- 1) 18 years of age or older, and
- 2) Receiving care for acute low back pain (i.e., does not meet the criteria for chronic LBP) during a primary care clinic visit.

An even distribution of age from 20-60 years of age is expected with a slight drop off after age 60, due to LBP becoming more of a chronic problem with aging. The lower age limit on recruitment of 18 years was included based on stakeholder feedback from internal medicine and family medicine colleagues that pointed out the different nature of LBP in adolescents. Gender is expected to be 50% male and race/ethnicity will closely match those in the geographical location of the sites. English language proficiency will not be an inclusion criterion because it is assumed that clinics with a significant non-English population will have translation capabilities for that population.

### 4.2 Exclusion criteria

Exclusion criteria are limited to medical contraindications to physical therapy based on the judgement of the PCP as documented in the EMR (i.e., “red flag” signs and symptoms of a potentially serious condition such as cauda equina syndrome, major or rapidly progressing neurological deficit, cancer, spinal infection or fracture).

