# 1 Study objectives

The target population for this study is adult patients who present to PCPs (i.e., internal medicine, family practice, and geriatric medicine physicians) to receive care for back pain during the primary care clinic visit. To distinguish “acute” versus “chronic” LBP, a 2-question screen based on criteria developed by the NIH Research Task Force on Chronic Low Back Pain will be used: 1) How long has low back pain interfered with your ability to do regular daily activities? 2) Think only about the past 6 months. How often has low back pain interfered with your ability to do regular daily activities? A response of “more than three months” to question 1, and a response of “half the days or more than half the days” to question 2 will define chronic LBP. By definition, all other patients will be defined as having acute LBP. Patients will be excluded who have medical contraindications to PT (“red flags”) based on the judgement of the PCP as documented in the EMR.

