- 2.3.4 **Pragmatic RCT comparing GBC and GBC+PIPT interventions:** This pragmatic RCT will have two study arms for treating patients identified as high risk for transitioning to chronic LBP: 1) GBC arm in which management decisions are made between PCPs and patients with the guidance of best evidence but with no specific directives, and 2) GBC+PIPT in which the PCP care includes directives for an immediate referral of high risk patients to a standardized regime of PIPT directed towards education and reduced fear of movement. By assessing the comparative effectiveness of GBC versus GBC+PIPT in an RCT conducted in the US, patients and their PCPs will be better able to judge the potential effectiveness of prompt referral to PIPT in reducing the risk of acute LBP leading to persistent disability from chronic LBP. Based on stakeholder feedback, an RCT design was chosen because its results will be more compelling and definitive, more generalizable with a greater degree of certainty that could lead to changes in provider behavior and payers' benefit design. This study's primary outcome (PRECIS-2 domain) of rate of transition from acute LBP to chronic LBP for high risk patients receiving PIPT is directly relevant to high risk acute LBP patients because it will address their specific psychosocial conditions and improve outcomes. Furthermore, it will provide PCPs with specific techniques for caring for these patients.
- 2.3.5 **Rationale for GBC comparator arm:** Based on guidance from Thompson and Schoenfeld, a comparator arm (GBC in this case) is justified because: 1) the research question is to compare an evidence-based "strategy" against guideline-informed care and 2) both approaches are considered prudent and good care for the target population. The "strategy" (GBC+PIPT) is an approach designed to match patients with LBP stratified to high risk to the PIPT regimen, which has been shown to be effective. In the GBC arm, PCPs will be given a primer on guidelines for LBP and have available through the EMR information about the patients' chronic versus acute status, functional limitations (Oswestry), and risk level (STarT Back). However, a PT referral will not be automatically generated and the PCP will have the freedom to treat high risk patients according to their individual clinical judgment.

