### 5.1 Interventions, administration, and duration

5.1.1 **Referral to PIPT:** As a result of the QI initiative, all patients in the intervention arm identified as high risk will be referred to PIPT. PCPs will have the results of the screening questionnaires in the EMR to identify the high risk acute LBP patients and refer them to PIPT. PCPs will provide patient education materials as appropriate, including materials about musculoskeletal injury, PT, and pain management. Referrals will occur through automatic electronic referral, manual electronic referral, written prescription, fax, or verbal means.

5.1.2 **Delivery of PIPT:** Upon referral to PIPT, trained physical therapists will use the PIPT approach with the high risk patients. The number of PT sessions recommended by the physical therapist will be based on their clinical judgment. Physical therapists will complete a checklist based on PT standards of care (see Appendix 4 based on Guide to Physical Therapy Practice <http://guidetoptpractice.apta.org/>) that will reflect the elements of the treatment provided. This checklist will be sent to the PCP and entered into the EMR. This

checklist will allow tracking of how many patients have received the prescribed physical therapy (i.e., a completed checklist, number of PT sessions).

- 5.1.3 **Patient-centered PIPT discharge instructions:** Community discussions with patients emphasized the desire to have a home exercise program in place after physical therapy that is feasible, effective, and sustainable. As an adjunct to the PIPT program, physical therapists can provide patients at discharge printed instructions for home practice exercises and a list of recommended community-based exercise classes and resources appropriate for the patient.
- 5.1.4 **Patient-reported outcomes:** At 6 months for all sites, lists of eligible patients will be generated from the EMR and patients will be contacted by research assistants by phone, email, or postal mail. This procedure is a modest departure from the pragmatic approach (PRECIS-2 follow-up domain); however, stakeholders indicated that 6-month assessments of this nature were not normal practice for the PCP clinics. These assessments will be for the Chronic LBP Questionnaire and Oswestry.

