- A total sample size of at least 8,760 participants is needed from these sites to meet the aims of the study,
- The study needs to be conducted within the clinical setting (i.e., a pragmatic trial), which typically allows <15 minutes per patient visit; the consent/authorization procedures would disrupt the clinical setting and potentially impact patient care.

6.2.3 **Enrollment and baseline evaluation:** Upon determination of eligibility, patients will be enrolled in the QI initiative of the study. Baseline data will be contained in the EMR and extracted for study purposes, including screening results, demographic information, billing information, and clinical data (e.g., diagnoses, referrals to specialists). Patients identified as high risk, acute LBP patients in the intervention arm will be referred to PIPT, and this referral will also be captured in the EMR. The list of baseline variables to be extracted from the EMR is provided in Appendix 6.

6.2.4 **Randomization:** As a cluster RCT, randomization will occur at the clinic level and not the patient level; therefore, randomization is not a factor in the enrollment or baseline evaluation.

6.2.5 **Follow-up:** Follow-up to the initial screening and QI enrollment visit will occur through three mechanisms:

- 1) **Referral to PIPT:** For eligible patients referred to PIPT, follow up at PT will be evaluated through the checklist completed at the PT visit and returned to the PCP site. This checklist will indicate use of the PIPT approach and number of PT sessions.
- 2) **Six-month assessment:** Research staff will contact all enrolled patients 6 months after their initial visit at all sites and conduct the Chronic LBP Questionnaire and the Oswestry to assess the primary outcomes.
- 3) **Medical resource utilization:** Researchers will also extract data from the EMR at select sites to determine the secondary outcome of LBP-related medical resource utilization of tests, procedures, and pharmaceuticals by enrolled patients for 12 months after the initial visit.

The list of variables for medical resource utilization is provided in Appendix 6.

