## 9.2 Randomization, sample size and power – RCT cohort

- 9.2.1 **Randomization** will occur at the clinic level, which was chosen for the pragmatic reason that randomizing patients within a clinic would result in cross contamination of the interventions within the same clinic. The biostatisticians and the individuals conducting the 6-month assessments will be blinded to the randomization assignment to avoid bias in analyses and data capture.
- 9.2.2 **Sample size** is based on the first primary outcome of the transition rate to chronic LBP at month 6. We propose to enroll N=1860 high risk acute LBP patients. We are targeting an average of n=31 enrolled high risk patients per clinic ( $60 \times 31 = 1860$ ) to account for the variation in cluster sizes (assuming coefficient of variation=0.65) and 40% non-response rate at 6 months.
- 9.2.3 **Power:** With a total of 60 PCP clinics for randomization, m=30 clinics per intervention strategy and fixed n=10-14 completers per clinic for the 6-month assessment, we will have just over 80% power to detect a 40% reduction in transition to chronic LBP assuming the control arm has a transition rate of 25%-30% and the intraclass correlation is 0.05, which is an upper bound for what has been observed in other cluster randomized trials with respect to either pain or LBP. Assuming that low and medium risk subjects with acute LBP have an expected 20% transition to chronic and using data on obesity and smoking rates based on national surveys, depression rates based on prevalence rates reported in primary care, and proportions of underserved patients estimated from patient registries at each of the five regional sites, the planned sample size for the observational cohort is sufficient to detect at least a 30% relative difference (6% absolute difference) from 20% with powers ranging from 79% to 87%. The study would have 65% power to detect a 40% relative or 8% absolute difference (hypothesized increased rate of transition) for the depression subgroup.

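### The only listed exclusion is a PCP judgement made after clinic allocation, with a referral prompt in one arm only, so marginal cases could be excluded unevenly

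*Combined protocol and SAP*

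**What the plan says.** Section 4.2 has a single exclusion criterion: "medical contraindications to physical therapy based on the judgement of the PCP as documented in the EMR". It gives examples of serious red-flag conditions, introduced as examples and not as a closed list. Section 1 repeats the rule: "Patients will be excluded who have medical contraindications to PT".

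On allocation and blinding, section 6.2.4 says that "randomization will occur at the clinic level and not the patient level". Section 9.2.1 says that "The biostatisticians and the individuals conducting the 6-month assessments will be blinded to the randomization assignment". PCPs are not mentioned there, and Table 1 and section 5.2.1 show that staff in intervention clinics are trained and coached on referral.

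On referral, the arms differ:
- **GBC+PIPT:** section 5.1.1 says that "all patients in the intervention arm identified as high risk will be referred to PIPT". Section 2.3.7 adds alerts, order sets and reports that track referral performance.
- **GBC:** section 2.3.5 says that "a PT referral will not be automatically generated", and section 5.2.1 leaves normal procedures unchanged apart from data collection.

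On enrollment, section 4.3.2 promises the same procedure in both arms. Section 4.3.1 admits everyone presenting with acute back pain, and section 6.2.1 makes acute status the test of eligibility. Neither says where the PCP exclusion comes in. Section 4.3.4 requires chronic cases and screening refusals to be documented, but does not mention red-flag exclusions.

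**The concern.** In a cluster trial, patients are recruited after their clinic's arm is known. Any patient-level eligibility decision that involves judgement, and is made by someone who knows the arm, can therefore select different patients into the two arms. Section 3.2 shows awareness of this: selection bias was one reason for rejecting individual randomization. Yet section 10.3.1 names only site selection and missing data as major sources of bias.

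Here the judgement concerns fitness for the very treatment that one arm is required to offer. A PCP in an intervention clinic who is prompted and monitored on referral has a reason to record a contraindication in a marginal case. A PCP in a GBC clinic has no equivalent prompt. If patients thought unfit for PT tend to do worse, uneven recording would make the intervention arm look better on both primary outcomes. Because these exclusions are not among those to be documented, an imbalance could go unseen.

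**Working it through.** **1. The plan's own figure.** Section 9.2.3 claims just over 80% power with 30 clinics per arm, 10-14 completers per clinic, intraclass correlation 0.05 and a 40% relative reduction from 25%-30%. Two-sided 5% is assumed; the documents state it only for the observational cohort (Table 3).

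Effective N per arm = 30n / (1 + (n - 1) × 0.05).
- n = 10: 300 / 1.45 = 206.9. For 30% against 18%, power is 81.8%.
- n = 14: 420 / 1.65 = 254.5. For 25% against 15%, power is 80.7%.

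The claim is reproduced at these pairings, so the variance basis used below is the plan's own.

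**2. Standard error at planned enrollment.** Section 9.2.2 gives 31 enrolled per clinic, 40% non-response and a coefficient of variation of cluster size of 0.65.
- Completers per clinic: 31 × 0.6 = 18.6.
- Design effect: 1 + ((0.65² + 1) × 18.6 - 1) × 0.05 = 2.27.
- Effective N per arm: 30 × 18.6 / 2.273 = 245.5.
- Standard error of the difference at 25% in both arms: √(2 × 0.25 × 0.75 / 245.5) = 0.0391.

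**3. Bias from one-sided exclusion.** Assume no true effect and a chronic rate of p = 25% in both arms. Let a fraction x of high-risk patients be excluded in the intervention arm only, with chronic rate r among them. The documents give neither x nor r; both are assumptions.

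Rate among those who remain = (p - x·r) / (1 - x), so the spurious benefit is b = x(r - p) / (1 - x).

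One-sided chance of a false significant result favouring PIPT = Φ(-1.96 + b / 0.0391), with b entered as a positive benefit. With b = 0 this is 2.5%.

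| x | r = 40%: b (points), tail | r = 60%: b (points), tail |
|---|---|---|
| 2% | 0.3, 3.0% | 0.7, 3.8% |
| 5% | 0.8, 3.9% | 1.8, 6.8% |
| 10% | 1.7, 6.3% | 3.9, 16.7% |

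For example, at x = 2% and r = 60%: (0.25 - 0.012) / 0.98 = 0.2429, a benefit of 0.7 points.

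**4. What moves the result.** The planned effect is 40% of 25%-30%, or 10-12 points. At x = 2% the bias is therefore 3-7% of a 10-point effect. A harsher r of 80% at x = 2% gives 0.02 × 0.55 / 0.98 = 1.1 points. If GBC clinics exclude similar patients too, the biases largely cancel and only the difference in exclusion matters. If excluded patients did better than average (r below p), the sign reverses.

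**The case against.** The case on the other side is substantial and narrows the point.

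- **Referral is not a one-arm decision.** A reader might infer that only intervention clinics have to decide about PT. Section 5.1.1 says otherwise: "Referrals will occur through automatic electronic referral, manual electronic referral, written prescription, fax, or verbal means". An automatic referral may need no PCP decision, and section 2.3.5 expects some GBC patients to be referred to PT. This reduces the asymmetry, but the duty, alerts and monitoring remain in one arm only.
- **Declining referral is not exclusion.** A reader might infer that a patient judged unsuitable for referral drops out of the trial. No section says so. Section 6.2.3 puts eligibility and enrollment before referral, and section 8 keeps enrollees who depart from the intended care. That protects patients already enrolled; it does not cover someone recorded as contraindicated when eligibility is settled.
- **The criterion is the same in both arms and tied to serious conditions.** Clear cases should be recorded everywhere. The risk lies in marginal cases, because the list is open and the test is judgement.
- **Other safeguards.** Identical enrollment is promised without a mechanism. Baseline comparison and adjustment for Oswestry, pain coping and psychiatric comorbidity (9.2.5, 9.5.1) can offset selection only so far as those covariates capture it, and act only on patients who remain. Blinded statisticians and assessors do not touch eligibility.

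**Conclusion.** The design leaves room for differential exclusion: a judgement-based criterion, applied patient by patient after allocation, by PCPs who are not listed as blinded, with a prompt in one arm only. That PCPs know their arm and that allocation comes first are inferences from the design, but strong ones.

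Two stronger readings are not supported. The plan does not contradict its intention-to-treat statement, because a criterion worded identically for both arms is compatible with it; uneven application would undermine the comparison. Nor do the documents show that the trial favours PIPT. Nothing in them gives the exclusion rate, its difference between arms or the prognosis of those excluded.

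If red flags are rare, the bias is small: about 0.3-0.7 points at an assumed 2% one-sided exclusion with chronic rates of 40-60%. The 5% and 10% rows matter only if exclusions are much commoner, with none in GBC. The direction is likely, not certain. The point merits action because the remedy is modest and the present rule would not reveal a problem if there were one.

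**What to change.** 1. In sections 4.2 and 9.2.5, define the RCT analysis set from the baseline screen: acute and STarT Back high risk. Section 6.2.1 has this completed in the seven days before the visit or on arrival, so the set can be fixed before the PCP's judgement. State that a patient not referred to PT on PCP judgement alone stays in the intention-to-treat set.
2. Apply the red-flag exclusion by one programmed EMR rule covering the conditions section 4.2 names, identically in both arms and without knowledge of arm. Use diagnoses recorded before the index visit; codes entered at that visit come from the same unblinded PCP under the same prompt.
3. Add a sensitivity analysis that keeps all screened acute high-risk patients, and report red-flag exclusions by arm and clinic.
4. Reconcile section 4.2 with sections 4.3.1, 4.3.4 and 6.2.1 on when the exclusion is applied and how it is recorded.

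The PCP's freedom over referral is unchanged, and so is the planned N. The cost is wording and an EMR code list. Appendix 6 lists comorbid conditions but no red-flag variable, so the sites should confirm that earlier diagnoses can be extracted. A fixed list also narrows a criterion that now covers signs and symptoms. A few patients whose red flags are first found at the visit would remain in both arms, with slight dilution of the effect.

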### 4.3 Study enrollment procedures

4.3.1 **Subjects will be enrolled** at all of the PCP clinics selected for the trial. In keeping with the pragmatic nature of the trial, all patients will be admitted into the trial who present with a complaint of acute back pain. Recruitment (PRECIS-2 domain) is highly pragmatic being solely based on patients presenting to the clinic with back pain.

4.3.2 **Randomization:** The study is a cluster RCT; randomization of treatment arm assignment is at the clinic level, not the individual patient. Enrollment will be the same for both arms of the study.

4.3.3 **Screening procedures:** Using patient portals, clinic-based tablets, or manual questionnaires, administrative staff or clinicians at the PCP sites will administer a baseline assessment with three components that will be included in the patients’ EMR. At all sites, the EMR will be modified to accept these data elements:

- 1) The 2-item Chronic LBP Questionnaire (Appendix 1),
- 2) The 9-item STarT Back Tool to stratify risk for transition to chronic LBP and identify high risk patients (Appendix 2),
- 3) The 10-item Oswestry LBP Questionnaire (Appendix 3).

4.3.4 **Ineligibility and non-participation:** Patients with chronic LBP will be documented as not eligible and will not be enrolled for intervention or subsequent assessments. Patients refusing to complete the baseline assessments will be documented as refusing screening and not included in the enrollment for intervention or subsequent assessments.

## 5 Study interventions

**Table 1: Study intervention components by study arms**

| Intervention components   | GBC | GBC+PIPT |
|---|-----|----------|
| Training of non-clinical and clinical staff at PCP offices on patient identification and data collection (QI)                       | ✓   | ✓        |
| PCP primer of LBP guidelines (QI)   | ✓   | ✓        |
| PCP and clinical staff instruction on stratification and referral to PIPT (QI)  |     | ✓        |
| Training for physical therapists on PIPT (QI)   |     | ✓        |
| Identification of LBP patients upon scheduling appointments or arrival in clinic (QI)   | ✓   | ✓        |
| LBP patient completion of questionnaires (Chronic LBP, STarT Back, Oswestry) (QI)   | ✓   | ✓        |
| Patient questionnaire results given to PCPs in EMR (QI)   | ✓   | ✓        |
| Acute LBP patient informed consent and enrollment in study for assessments at 6 months and review of medical record data (Research) | ✓   | ✓        |
| Acute LBP high risk patients referred to PIPT (QI)  |     | ✓        |
| Acute LBP high risk patients attend PIPT session (QI)   |     | ✓        |
| PT performs PIPT for acute LBP high risk patients (QI)  |     | ✓        |
| PT completes checklist and returns to PCP for acute LBP high risk patients (QI)   |     | ✓        |
| 6-month assessment for all acute LBP patients (Research)  | ✓   | ✓        |
| 12-month EMR resource use assessment for all acute LBP patients*(Research)  | ✓   | ✓        |
| *EMR data for UPMC, BMC, JHM, IH   |     |          |

### 5.1 Interventions, administration, and duration

5.1.1 **Referral to PIPT:** As a result of the QI initiative, all patients in the intervention arm identified as high risk will be referred to PIPT. PCPs will have the results of the screening questionnaires in the EMR to identify the high risk acute LBP patients and refer them to PIPT. PCPs will provide patient education materials as appropriate, including materials about musculoskeletal injury, PT, and pain management. Referrals will occur through automatic electronic referral, manual electronic referral, written prescription, fax, or verbal means.

5.1.2 **Delivery of PIPT:** Upon referral to PIPT, trained physical therapists will use the PIPT approach with the high risk patients. The number of PT sessions recommended by the physical therapist will be based on their clinical judgment. Physical therapists will complete a checklist based on PT standards of care (see Appendix 4 based on Guide to Physical Therapy Practice <http://guidetoptpractice.apta.org/>) that will reflect the elements of the treatment provided. This checklist will be sent to the PCP and entered into the EMR. This

checklist will allow tracking of how many patients have received the prescribed physical therapy (i.e., a completed checklist, number of PT sessions).

- 5.1.3 **Patient-centered PIPT discharge instructions:** Community discussions with patients emphasized the desire to have a home exercise program in place after physical therapy that is feasible, effective, and sustainable. As an adjunct to the PIPT program, physical therapists can provide patients at discharge printed instructions for home practice exercises and a list of recommended community-based exercise classes and resources appropriate for the patient.
- 5.1.4 **Patient-reported outcomes:** At 6 months for all sites, lists of eligible patients will be generated from the EMR and patients will be contacted by research assistants by phone, email, or postal mail. This procedure is a modest departure from the pragmatic approach (PRECIS-2 follow-up domain); however, stakeholders indicated that 6-month assessments of this nature were not normal practice for the PCP clinics. These assessments will be for the Chronic LBP Questionnaire and Oswestry.

